This study is a pilot trial investigating the feasibility of using activity monitoring data to adjust insulin pump therapy and prevent hypoglycemia. The study will enroll 20 patients 1-17 years old with type 1 diabetes mellitus on insulin pump therapy. Subjects will be provided with continuous glucose monitors (DexCom G4) and FitBit activity monitors. Study duration will be 3 to 4 months. During the course of the study patients will continue to receive routine care by their primary endocrinologist and DNE. Insulin dose adjustments unrelated to activity monitor data will continue to be at the discretion of the patient's primary diabetes team.

Activity level (steps and calories burned) will be uploaded over the web in a secure fashion to our central firewall-protected database on a daily basis while

CGM glucose values and insulin pump data will be collected once a week. Data from the activity monitor is automatically sent to a secure study team RedCap database once a day. This occurs by automatic, wireless syncing of the activity monitor with the patient/family's computer or smartphone. The activity monitor and activity monitor data is not associated with any personal health information. The activity monitor is only set up with a study identification number. Only study team members have access to the list of study identification numbers and associated patient information and this is stored in a secure computer a locked office. CGM and insulin pump data will be downloaded onto a patient or study team computer and then emailed to the study team once a week. Families will also have the option of coming to clinic once a week and having a study team member download the CGM and insulin pump data for them.

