The initial 2 weeks of a subject's enrollment in the study will be used to establish his or her baseline activity level and no changes to the insulin regimen will be made based on the activity monitor data. During weeks 3-6 to 12-16, activity data will be reviewed daily and an alternate basal insulin rate will be recommended on days considered to be increased activity days. We will use an adaptive algorithm to help guide suggested nighttime insulin basal rate changes. All recommendations will be reviewed and approved by a study physician prior to implementation. The alternate rate will be derived using the subject's usual care pump settings as an initial starting point from which to make incremental changes in the 3 hour interval leading up to the hypoglycemic event. Target will be the overnight nadir obtained with usual care settings. Residual error (CGM-target) will be used to assess the validity of using the 3 hour window prior to the event to effect lower basal. The patient's primary diabetes team will be informed about the recommended nighttime basal insulin dose change and this will be documented in the patient's medical record in powerchart. The primary diabetes team will not give recommendations regarding nighttime insulin rate dose changes based on activity monitor data; however, they will continue to guide all other aspects of the patient's diabetes management.

b. Patient Selection and Inclusion/Exclusion Criteria

Subjects will be recruited from the outpatient endocrinology clinic based on physician recommendation and approval to approach at Boston Children's Hospital (BCH) as well as through public notice. 20 subjects will be recruited in two different age designations.

Inclusion Criteria:

- Age: 1 to 17 years old
- Type 1 diabetes (as clinically diagnosed by outpatient endocrinologist).
- Treated with insulin pump therapy for greater than or equal 3 months

- Families will need to have access to Wi-Fi and a compatible smartphone in order for the data from the activity monitor and other devices to be transmitted to the research team

Exclusion Criteria:

- Current glucocorticoid use or other medication known to affect insulin action at investigator's discretion.
- Hospitalization within the last month

c. **Description of Study Treatments and Procedures**

RECRUITMENT, SCREENING AND CONSENT:

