This is a pilot study to determine the feasibility of combining activity monitor data with CGM and pump data to make prospective recommendations to reduce basal insulin delivery following high activity days. There is no planned hypothesis for the pilot phase; however, planned comparisons for a larger study will be powered from the data obtained. The primary endpoint for the larger study will be a reduction in the incidence of nighttime hypoglycemia. Secondary outcomes will include the ability of activity data to predict nighttime nadir glucose.

Hypoglycemia will be defined as home meter glucose < 70 mg/dl for all subjects, CGM values below threshold for >30 minutes with no concomitant blood sugar reading (i.e. subject is sleeping at home and ignores the low glucose

alarm but the CGM is <70 for more than 30 minutes). Hypoglycemia episodes within one hour of each other will be considered as one event. Two hypoglycemic events with an intermittent blood glucose value above 70 mg/dL will be treated as a single event. Hypoglycemia and “use-of-supplemental- carbohydrate-to-prevent-hypoglycemia” will be treated identically.

5. Data Management and Statistical Analysis

One study folder, with IRB approved consent forms and case report forms (CRF), will be maintained for each subject recruited into the study. Sensor information, as provided by the manufacturer, will also be recorded on CRFs (identification numbers such as lot or serial together with expiration). Electronic data downloads for the insulin pump, containing a history of insulin delivery commands; glucose meter and glucose sensor, containing a record of all glucose values received and any alarms will be obtained weekly and the downloaded files copied to a password protected study computer in subdirectory labeled with the patient identification number. A copy of the spreadsheet used to screen blood glucose and activity data will also be placed in this directory.

a. Data Analysis Plan

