Data analysis will begin by calculating the baseline (average and standard deviation) activity level for each subject during the first two to six weeks. High activity days will be defined as any day where the activity is greater than one standard deviation above the mean. Correlations will be performed to assess if there is relationship between daytime activity (8- am to 9 pm) and nighttime nadir blood glucose level (continuous). Nadir glucose will also be categorized as hypo- or no-hypo (binary), with a binary logistic regression model used to assess the significance of daytime activity, insulin dosing, and carbohydrate intake, as independent factors increasing the risk of hypoglycemia. Analysis will proceed with generalized estimating equations (not powered but in preparation of the larger study to be conducted). Characteristics of the nighttime glucose profile (nadir glucose, time in target, time below target) will be calculated weekly, with mean and 95% confidence plotted by week. In the event usual-care pump settings are adjusted during the course of the study, the average nighttime glucose values observed for the week following the most recent adjustment will be compared to average values obtained during the final week (assures improvements are due to the availability of the FitBit data rather than the CGM data). Chi2 analysis will be used to assess differences in the incidence of hypoglycemia. Statistical analyses will be performed both as intention to treat and per protocol. The intention to treat analysis will include all data; per protocol analysis will exclude cases in which the subject does not comply with recommendations of the study team or does not complete all 12 weeks of the study. The algorithm will be considered feasible if all data can be assembled, and recommendations deemed reasonable (accepted) in a majority of cases.

Statistical Power and Sample Considerations

This is a feasibility study and therefore is not powered; however, the choice of 10 subjects with any one group is generally considered acceptable for feasibility/pilot-studies and should provide sufficient data to power a larger study.

Study Organization

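### The chi-square named for hypoglycemia incidence has no stated contrast, unit or pairing, and an unpaired chi-square does not fit repeated nights from the same 20 children

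*Combined protocol and SAP*

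**What the plan says.** Section 5.a (Data Analysis Plan) treats hypoglycemia as a yes/no outcome in two places.

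- A regression, "with a binary logistic regression model used to assess the significance of daytime activity, insulin dosing, and carbohydrate intake, as independent factors", followed by: "Analysis will proceed with generalized estimating equations (not powered but in preparation of the larger study to be conducted".
- Three sentences after the regression, on its own: "Chi2 analysis will be used to assess differences in the incidence of hypoglycemia".

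The chi-square sentence gives no contrast, no unit of analysis, and no allowance for pairing or clustering. The sentence before it compares average nighttime glucose in the week after the latest usual-care adjustment with the final week, but the chi-square is not tied to that comparison.

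On design, section 4.a says: "The study will enroll 20 patients 1-17 years old with type 1 diabetes mellitus on insulin pump therapy". It adds: "Study duration will be 3 to 4 months". There is no control group. Section 4.d states that the pilot has no planned hypothesis, that the larger study's primary endpoint will be a reduction in nighttime hypoglycemia, and that "planned comparisons for a larger study will be powered from the data obtained".

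**The concern.** A Pearson chi-square compares independent observations in separate groups. Here each child supplies many nights, and every child contributes to both the early and the late period, and to both high-activity and other nights. Neither condition holds for the comparisons this design can make.

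The error has no fixed direction. If children differ only in a stable level of risk, an unpaired test leaves that variation in its standard error although the within-child contrast removes it, so the test is too cautious. If a child's risk shifts from one period to the next, the test counts that shift as many independent nights of evidence and rejects too often. Shifts are likely: primary teams go on adjusting insulin, the study team may act on nocturnal hyperglycemia, and intercurrent illness is asked about weekly (section 4.c).

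At stake are a misleading p-value for incidence and, more importantly, a pilot summary that omits the between-child and child-by-period variance needed to size the larger study.

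**Working it through.** **Inputs from the documents.** There are 20 children (section 4.a). A 12-week study (section 5.a) gives 12 x 7 = 84 nights per child and 20 x 84 = 1,680 child-nights. An initial 2-week baseline (section 4.a) gives 14 nights, leaving 84 - 14 = 70. A weekly comparison is 7 v 7 nights.

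**Assumed inputs.** The documents give no nightly rate, no within-child correlation and no alpha. I assume about 20% of nights with hypoglycemia, a between-child SD of 0.8-1.2 on the logit scale, and a two-sided 5% level. The plan has no figure of its own to reproduce.

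**Step 1: nights as the unit.** For each child and period,

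y ~ Binomial(nights, expit(-1.6 + child effect + child-by-period effect)),

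with no true mean difference. Each setting was simulated 20,000 times. The pooled nights were tested by Pearson chi-square, and the 20 within-child rate differences by a paired t-test.

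| Contrast | Child-by-period SD | Chi-square type I error |
|---|---|---|
| 7 v 7 nights | 0 | 3-4% |
| 14 v 70 nights | 0 | 3-4% |
| 7 v 7 nights | 0.5-0.8 | 6-10% |
| 14 v 70 nights | 0.5-0.8 | 12-25% |

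The paired t-test on the same data stayed at about 5%.

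**Step 2: a second model as a check.** Beta-binomial nights were used, with nightly rates of 0.10-0.30 and an intra-child correlation (ICC) of 0.05, 0.10 or 0.20.

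- Stable child risk, same children in both periods: 2.8-4.8%.
- 14 v 70 nights, child risk half correlated between periods: about 11%, 17% and 27% at the three ICC values.
- High-activity v other nights, with the high-activity share assumed to vary from 5% to 35% between children and stable risk: about 7%, 9-10% and 13-14%.
- ICC of 0: about 5% throughout, as it should be.

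The two models agree in direction and roughly in size.

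**Step 3: children as the unit, before and after.** Nights are no longer pooled, but each child appears in both columns, so the table is paired and a Pearson chi-square ignores this. Unequal periods add a bias. With a nightly rate of 0.10 and ICC 0.10, the beta parameters are a = 0.9 and b = 8.1, and P(any event in m nights) = 1 - B(a, b + m)/B(a, b). This gives about 60% for m = 14 and 87% for m = 70, with no change in risk.

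**Step 4: consequence for planning.** For an overall incidence rate, the design effect is 1 + (m - 1) x ICC. At m = 84 it is 1 + 83 x 0.05 = 5.15, 1 + 83 x 0.10 = 9.3, or 1 + 83 x 0.20 = 17.6. The 1,680 child-nights then carry the information of 1,680/5.15 = 326, 1,680/9.3 = 181, or 1,680/17.6 = 95 independent nights. A pooled table shows none of this.

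**The case against.** The strongest reply is that the plan does not ignore correlation. It names GEE in the same paragraph, for the same binary outcome, and ties it to the larger study. That stands as far as it goes: the chi-square is not the only analysis of hypoglycemia. But the GEE sentence follows a model whose listed factors are activity, insulin dosing and carbohydrate intake. With no term for period or for use of a recommendation, that model does not clearly answer whether incidence changed.

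A reader might infer that the plan commits to pooling nights as independent. It does not say so; the unit is unstated. The objection to an unpaired test survives because counting children before and after fails too, for a different reason.

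A reader might also extend the point to the weekly confidence limits or to a comparison of age groups. The documents support neither. A chi-square produces no interval, the weekly limits describe glucose characteristics, and section 5.a plans no age-group comparison of hypoglycemia.

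Finally, the larger error rates need assumed drift. For week versus week, the contrast closest to the chi-square sentence, the error is modest. This is correct, and the figures should be read as a range.

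**Conclusion.** The point holds. The only method named for differences in hypoglycemia incidence lacks a contrast and a unit, and in its ordinary unpaired form it is invalid for any period or high-activity comparison in this single-arm design.

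On the assumed rate and between-child spread, the true error rate at nominal 5% runs from about 3-4% (stable child risk) to 6-10% (week v week) or 12-25% (14 v 70 nights) with child-by-period SD 0.5-0.8. The documents cannot narrow that range.

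It would go too far to say that this undermines the pilot's conclusions. The pilot has no planned hypothesis and is not powered, and feasibility is judged on assembling the data and on recommendations being accepted. Nor is the larger study's planning bound to the chi-square result: the night-level records would still allow clustering to be estimated. The correction is worth making because incidence is the endpoint to be carried forward and the change is cheap.

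**What to change.** Replace the chi-square sentence with a stated contrast and a within-child analysis. For example:

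*The incidence contrast is [baseline v later nights, or the week after the last usual-care adjustment v the final week]. For each child, the number of hypoglycemic nights per valid night is computed on each side. The mean within-child difference is reported with a paired 95% confidence interval, with degrees of freedom equal to evaluable children minus 1.*

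Alternatively, extend the planned GEE to this contrast, with child as the cluster, a period or activity term, and a small-sample correction for about 20 clusters. The paired version weights every child equally, however few nights that child has on one side; if flagged nights are sparse, that favours GEE.

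Two details need settling at the same time: what counts as a valid night, and how long baseline lasts, since section 4.a says 2 weeks while sections 4.c and 5.a allow two to six.

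Also report the between-child and child-by-period variance of the nightly rate for planning the larger study.

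The cost is a few sentences and slightly more programming, with no new data. Some p-values or intervals will be less favourable than a pooled chi-square would suggest.
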